**TABLE 2. ADVERSE DRUG REACTIONS REQUIRING AVELUMAB DISCONTINUATION OR MODIFICATION**

Dose escalation or reduction is not recommended. Dosing delay or discontinuation may be required based on individual safety and tolerability (refer to [Appendix 6](#)). Resume avelumab in patients whose adverse reactions recover to Grade 1 or resolved.

**Any Grade 4 ADRs require permanent treatment discontinuation with avelumab** except for single laboratory values out of normal range that are unlikely related to study treatment as assessed by the Investigator, do not have any clinical correlate, and resolve within 7 days with adequate medical management and endocrinopathies controlled with hormone replacement.

**Any Grade 3 ADRs require treatment discontinuation with avelumab except for any of the following:**

- Transient ( $\leq$  6 hours) Grade 3 flu-like symptoms or fever, which is controlled with medical management
- Transient ( $\leq$  24 hours) Grade 3 fatigue, local reactions, headache, nausea, emesis that resolves to Grade  $\leq$  1
- Single laboratory values out of normal range (excluding Grade  $\geq$  3 liver function test increase) that are unlikely related to study treatment according to the Investigator, do not have any clinical correlate, and resolve to Grade  $\leq$  1 within 7 days with adequate medical management
- Tumor flare phenomenon defined as local pain, irritation, or rash localized at sites of known or suspected tumor
- Change in ECOG PS to  $\geq$  3 that does not resolve to  $\leq$  2 within 14 days (infusions should not be given on the following cycle, if the ECOG PS is  $\geq$  3 on the day of study drug administration)

**Recurrent Grade 3 ADRs and Grade 3 infusion-related reaction require permanent discontinuation.**

**Any Grade 2 ADR should be managed as follows:**

- If a Grade 2 ADR resolves to Grade  $\leq$  1 by the last day of the current cycle, treatment may continue.
- If a Grade 2 ADR does not resolve to Grade  $\leq$  1 by the last day of the current cycle, infusions should not be given on the following cycle. If at the end of the following cycle the event has not resolved to Grade 1, it should be treated as a Grade 3 or 4 (except for hormone insufficiencies, that can be managed by replacement therapy; for these hormone insufficiencies, up to 2 subsequent doses may be omitted).
- Upon the second occurrence of the same Grade 2 ADR (except for hormone insufficiencies that can be managed by replacement therapy) in the same subject, treatment with avelumab has to be permanently discontinued.

**TABLE 3. TREATMENT MODIFICATION FOR SYMPTOMS OF INFUSION-RELATED REACTIONS**

NCI-CTCAE Grade	Treatment Modification for avelumab
Grade 1 – mild Mild transient reaction; infusion interruption not indicated; intervention not indicated.	Decrease the study drug infusion rate by 50% and monitor closely for any worsening.
Grade 2 – moderate Therapy or infusion interruption indicated but responds promptly to symptomatic treatment (for example, antihistamines, NSAIDs, narcotics, IV fluids); prophylactic medications indicated for $\leq 24$ h.	Temporarily discontinue avelumab infusion. Resume infusion at 50% of previous rate once infusion-related reaction has resolved or decreased to at least Grade 1 in severity, and monitor closely for any worsening.
Grade 3 or Grade 4 – severe or life-threatening Grade 3: Prolonged (for example, not rapidly responsive to symptomatic medication and/or brief interruption of infusion); recurrence of symptoms following initial improvement; hospitalization indicated for clinical sequelae. Grade 4: Life-threatening consequences; urgent intervention indicated.	Stop avelumab infusion immediately and disconnect infusion tubing from the subject. Subjects have to be withdrawn immediately from avelumab treatment and must not receive any further avelumab treatment.

IV = intravenous; NCI-CTCAE = National Cancer Institute-Common Terminology Criteria for Adverse Event; NSAIDs = nonsteroidal anti-inflammatory drugs.

**TABLE 4. MANAGEMENT OF IMMUNE-MEDIATED ADVERSE REACTIONS**

Since inhibition of PD-L1 stimulates the immune system, immune-related AEs (irAEs) may occur. Treatment of irAEs is mainly dependent upon severity (NCI-CTCAE version 4.03 grade)

Grade 1 to 2: treat symptomatically or with moderate dose steroids, more frequent monitoring

Grade 1 to 2 (persistent): manage similar to high grade AE (Grade 3 to 4)

Grade 3 to 4: treat with high dose corticosteroids

Treatment of gastrointestinal, dermatological, pulmonary, hepatic, renal, cardiac, endocrine or other irAEs should follow guidelines set forth in the table below.

Gastrointestinal irAEs		
Severity of Diarrhea / Colitis	Initial Management	Follow-up Management
Grade 1 Diarrhea: < 4 stools/day over Baseline Colitis: asymptomatic	Continue avelumab therapy Symptomatic treatment (for example, loperamide)	Close monitoring for worsening symptoms Educate subject to report worsening immediately If worsens: Treat as Grade 2 or 3/4
Grade 2 Diarrhea: 4 to 6 stools per day over Baseline; IV fluids indicated < 24 hours; not interfering with ADL Colitis: abdominal pain; blood in stool	Withhold avelumab therapy Symptomatic treatment	If improves to Grade $\leq 1$ : Resume avelumab therapy.  If persists > 5 to 7 days or recur: Treat as Grade 3 to 4
Grade 3 to 4 Diarrhea (Grade 3): $\geq 7$ stools per day over Baseline; incontinence; IV fluids $\geq 24$ hrs.; interfering with ADL Colitis (Grade 3): severe abdominal pain, medical intervention indicated, peritoneal signs	Withhold avelumab for Grade 3.  Permanently discontinue avelumab for Grade 4 or recurrent Grade 3.  1.0 to 2.0 mg/kg/day prednisolone IV or equivalent	If improves: Continue steroids until Grade $\leq 1$ , then taper over at least 1 month; resume avelumab therapy following steroids taper (for initial Grade 3).  If worsens, persists > 3 to 5 days, or recurs after improvement:

Grade 4: life-threatening, perforation	Add prophylactic antibiotics for opportunistic infections  Consider lower endoscopy	Add infliximab 5 mg/kg (if no contraindication).  Note: Infliximab should not be used in cases of perforation or sepsis.
--	---	--

### Dermatological irAEs

Grade of Rash	Initial Management	Follow-up Management
Grade 1 to 2  Covering $\leq$ 30% body surface area	Continue avelumab therapy  Symptomatic therapy (for example, antihistamines, topical steroids)	If persists $>$ 1 to 2 weeks or recurs:  Withhold avelumab therapy Consider skin biopsy   Consider 0.5 to 1.0 mg/kg/day prednisolone or equivalent. Once improving, taper steroids over at least 1 month, consider prophylactic antibiotics for opportunistic infections, and resume avelumab therapy following steroids taper.  If worsens:  Treat as Grade 3 to 4.
Grade 3 to 4  Grade 3: Covering $>$ 30% body surface area;  Grade 4: life threatening consequences	Withhold avelumab for Grade 3.  Permanently discontinue for Grade 4 or recurrent Grade 3. Consider skin biopsy Dermatology consult 1.0 to 2.0 mg/kg/day prednisolone or equivalent Add prophylactic antibiotics for opportunistic infections.	If improves to Grade $\leq$ 1:  Taper steroids over at least 1 month; resume avelumab therapy following steroids taper (for initial Grade 3)

### Pulmonary irAEs

Grade of Pneumonitis	Initial Management	Follow-up Management
Grade 1	Consider withholding avelumab therapy	Re-assess at least every 3 weeks  If worsens:

Radiographic changes only	Monitor for symptoms every 2 to 3 days Consider Pulmonary and Infectious Disease consults	Treat as Grade 2 or Grade 3 to 4.
Grade 2 Mild to moderate new symptoms	Withhold avelumab therapy Pulmonary and Infectious Disease consults Monitor symptoms daily, consider hospitalization 1.0 to 2.0 mg/kg/day prednisolone or equivalent followed by a corticosteroid taper. Add prophylactic antibiotics for opportunistic infections Consider bronchoscopy, lung biopsy	Re-assess every 1 to 3 days If improves: When symptoms return to Grade $\leq 1$ , taper steroids over at least 1 month and then resume avelumab therapy following steroids taper If not improving after 2 weeks or worsening: Treat as Grade 3 to 4.
Grade 3 to 4 Grade 3: Severe new symptoms; New / worsening hypoxia; Grade 4: life-threatening	Permanently discontinue avelumab therapy Hospitalize. Pulmonary and Infectious Disease consults. 1.0 to 2.0 mg/kg/day prednisolone or equivalent followed by a corticosteroid taper Add prophylactic antibiotics for opportunistic infections Consider bronchoscopy, lung biopsy	If improves to Grade $\leq 1$ : Taper steroids over at least 1 month. If not improving after 48 hours or worsening: Add additional immunosuppression (for example, infliximab, cyclophosphamide, IV immunoglobulin, or mycophenolate mofetil)
Hepatic irAEs		
Grade of Liver Test Elevation	Initial Management	Follow-up Management
Grade 1 Grade 1 AST or ALT $>$ ULN to 3.0 x ULN and/or total bilirubin $>$ ULN to 1.5 x ULN	Continue avelumab therapy	Continue liver function monitoring If worsens: Treat as Grade 2 or 3 to 4
Grade 2	Withhold avelumab therapy	If returns to Grade $\leq 1$ :

AST or ALT $> 3.0$ to $\leq 5$ x ULN and / or total bilirubin $> 1.5$ to $\leq 3$ x ULN	Increase frequency of monitoring to every 3 days	Resume routine monitoring, resume avelumab therapy If elevations persist $> 5$ to 7 days or worsen: Treat as Grade 3 to 4.
Grade 3 to 4 AST or ALT $> 5$ x ULN and/or total bilirubin $> 3$ x ULN	Permanently discontinue avelumab therapy  Increase frequency of monitoring to every 1 to 2 days 1.0 to 2.0 mg/kg/day prednisolone or equivalent, followed by a corticosteroid taper  Add prophylactic antibiotics for opportunistic infections  Consult gastroenterologist/hepatologist  Consider obtaining MRI/CT scan of liver and liver biopsy if clinically warranted.	If returns to Grade $\leq 1$ : Taper steroids over at least 1 month  If does not improve in $> 3$ to 5 days, worsens or rebounds: Add mycophenolate mofetil 1 gram (g) twice daily  If no response within an additional 3 to 5 days, consider other immunosuppressants per local guidelines

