**For phase 1 and phase 2:**

- Age: Men and women aged  $\geq 18$  years,
- Signed written informed consent,
- Any histologic type of locally advanced or metastatic NSCLC,
- Life expectancy of  $\geq 12$  weeks,
- Measurable or evaluable (cytologically or radiologically detectable disease such as ascites, peritoneal deposits, or lesions which do not fulfill RECIST 1.1 criteria for measurable disease) lesions according to RECIST 1.1 criteria for phase 1 portion. For phase 2, all patients must have RECIST 1.1 measurable disease,
- PHYSIOLOGIC FUNCTION:
  - ✓ Hematologic: Absolute neutrophil count (ANC)  $\geq 1.5 \times 10^9/L$ , platelet count  $\geq 100 \times 10^9/L$ , and hemoglobin  $\geq 9$  g/dL (may have been transfused),
  - ✓ Hepatic: Total bilirubin level  $\leq 1.5 \times$  the upper limit of normal (ULN) range and AST and ALT levels  $\leq 2.5 \times$  ULN,
  - ✓ Renal: Estimated creatinine clearance  $\geq 30$  mL/min according to the Cockcroft-Gault formula (or local institutional standard method).
- PREGNANCY AND CONTRACEPTION:
  - ✓ Pregnancy test: Negative serum or urine pregnancy test at screening for women of childbearing potential.
  - ✓ Contraception: Highly effective contraception for both male and female subjects throughout the study and for at least 90 days after last treatment administration if the risk of conception exists.
- Ability to comply with protocol requirements,
- Willingness to consent and ability to undergo a trucut biopsy to obtain a fresh metastasis or primary tumor biopsy, and to undergo bronchoscopy to obtain a biopsy from normal bronchial mucosa,

- No serious or medically uncontrolled concomitant conditions that are likely to make the patient unfit for SPRING combination therapy, as per investigator assessment,
- ECOG performance status of 0 to 1.

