#### **4.2. EXCLUSION CRITERIA**

***Note: Exclusion criteria should be verified between consent and registration (28 days maximum window).***

- Patients with documented oncogenic aberrations at enrollment: EGFR, ALK, ROS1 when available, MET exon 14 skipping when available. For squamous undifferentiated cell carcinoma, documentation of these aberrations is not mandatory.

Note: For Phase 1 portion, all patients with adenocarcinoma histology must have documentation of results for druggable oncogenic aberrations (EGFR mutations, ALK rearrangements, and ROS1 when available) prior to enrollment on the study.

- For Phase 1 portion, >2 lines of prior therapy in the metastatic setting.
- For the dose escalation phase of the study or until the MTD for the combination regimen has been determined, patients with moderate hepatic impairment defined as AST, ALT, ALP >5 times ULN, which would be grade 3 or higher. However, patients with liver metastases with AST/ALT ≤ 5 x ULN can be included in the study.
- For Phase 2 portion, any prior therapy in the metastatic setting.

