### **5.6.2.13. Potential drug-induced liver injury (Hy's law cases)**

For Pfizer investigational (non-authorized) medicinal products and Pfizer products that are investigational in the United States (irrespective of being authorized elsewhere), interventional clinical study reports with elevations in aspartate aminotransferase (AST) and/or alanine aminotransferase (ALT) in addition to and/or preceding total bilirubin (TBili) elevations ( $>2 \times$  ULN) are considered potential drug-induced liver injury (DILI- assessed per Hy's law criteria) cases and should always be considered important medical events and should be reported as SAEs, even before all other possible causes of liver injury have been excluded.

The threshold of laboratory abnormalities for a potential DILI case depends on the subject's individual baseline values and underlying conditions. Subjects who present with the following laboratory abnormalities should be evaluated further as potential DILI (Hy's law) cases to definitively determine the etiology of the abnormal laboratory values:

- Subjects with AST/ALT and TBili baseline values within the normal range who subsequently present with AST or ALT values  $>3 \times$  ULN and a TBili value  $>2 \times$  ULN with no evidence of hemolysis and an alkaline phosphatase value  $<2 \times$  ULN or not available.
- For subjects with baseline AST or ALT or TBili values above the ULN, the following threshold values are used in the definition mentioned above, as needed, depending on which value(s) are above the ULN at baseline.
- Preexisting AST or ALT baseline values above the normal range: AST or ALT values  $>2$  times the baseline values and  $>3 \times$  ULN; or  $>8 \times$  ULN (whichever is smaller).
- Preexisting values of TBili above the normal range: TBili level increased from baseline value by an amount of at least  $1 \times$  ULN or if the value reaches  $>3 \times$  ULN (whichever is smaller).

Rises in AST/ALT and TBili separated by more than a few weeks are assessed individually based on clinical judgment; any case where uncertainty remains as to whether it might represent a potential DILI case is reviewed with the sponsor. The investigator coordinator is informed if such a situation occurs during the study and she will inform the HIC that will provide the necessary support for an appropriate evaluation.

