**TABLE 1. SAFETY RELATED INCLUSION AND EXCLUSION CRITERIA**

INCLUSION CRITERIA

1. AGE: Male or female subjects aged <math>\geq</math> 18 years.
 
2. PHYSIOLOGIC FUNCTION:  Hematologic: Absolute neutrophil count (ANC) <math>\geq 1.5 \times 10^9/L</math>, platelet count <math>\geq 100 \times 10^9/L</math>, and hemoglobin <math>\geq 9 \text{ g/dL}</math> (may have been transfused) (Applicable for solid tumors).  Hepatic: Total bilirubin level <math>\leq 1.5 \times</math> the upper limit of normal (ULN) range and AST and ALT levels <math>\leq 2.5 \times</math> ULN or AST and ALT levels <math>\leq 5 \times</math> ULN (for subjects with documented metastatic disease to the liver).  Renal: Estimated creatinine clearance <math>\geq 30 \text{ mL/min}</math> according to the Cockcroft-Gault formula (or local institutional standard method).
 
3. PREGNANCY AND CONTRACEPTION:  Pregnancy test: Negative serum or urine pregnancy test at screening for women of childbearing potential.  Contraception: Highly effective contraception for both male and female subjects throughout the study and for at least 60 days after last avelumab treatment administration if the risk of conception exists.

EXCLUSION CRITERIA

1. IMMUNOSUPPRESSANTS: “Current use of immunosuppressive medication, EXCEPT for the following: a. intranasal, inhaled, topical steroids, or local steroid injection (e.g., intra-articular injection); b. Systemic corticosteroids at physiologic doses <math>\leq 10 \text{ mg/day}</math> of prednisone or equivalent; c. Steroids as premedication for hypersensitivity reactions (e.g., CT scan premedication).”
 
2. AUTOIMMUNE DISEASE: “Active autoimmune disease that might deteriorate when receiving an immuno-stimulatory agent. Patients with diabetes type I, vitiligo, psoriasis, or hypo- or hyperthyroid diseases not requiring immunosuppressive treatment are eligible.”
 
3. ORGAN TRANSPLANTATION: “Prior organ transplantation including allogenic stem-cell transplantation.”
 
4. INFECTIONS: “Active infection requiring systemic therapy.”
 
5. HIV/AIDS: “Known history of testing positive for HIV or known acquired immunodeficiency syndrome.”

6. HEPATITIS: “Hepatitis B virus (HBV) or hepatitis C virus (HCV) infection at screening (positive HBV surface antigen or HCV RNA if anti-HCV antibody screening test positive)”

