#### Renal irAEs

Grade of Creatinine Increased	Initial Management	Follow-up Management
Grade 1 Creatinine increased $>$ ULN to 1.5 x ULN	Continue avelumab therapy	Continue renal function monitoring  If worsens: Treat as Grade 2 or 3 to 4.
Grade 2 to 3 Creatinine increased $> 1.5$ and $\leq 6$ x ULN	Withhold avelumab therapy.  Increase frequency of monitoring to every 3 days. 1.0 to 2.0 mg/kg/day prednisone or equivalent  Add prophylactic antibiotics for opportunistic infections.  Consider renal biopsy.	If resumes to Grade $\leq 1$ : Taper steroids over at least 1 month, and resume avelumab therapy following steroids taper.  If worsens: Treat as Grade 4.
Grade 4 Creatinine increased $> 6$ x ULN	Permanently discontinue avelumab therapy  Monitor Creatinine daily.	If resumes to Grade $\leq 1$ : Taper steroids over at least 1 month.

	
1.0 to 2.0 mg/kg/day prednisone or equivalent
 
Add prophylactic antibiotics for opportunistic infections.
 
Consider renal biopsy.
 
Nephrology consult.
	
--	---	--

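### If the 5 x ULN entry limit governs, a liver-metastasis patient with stable AST/ALT above 3 x ULN is eligible, yet unchanged values meet the withhold and then the permanent-stop rule of Appendix 6 Table 4

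*Combined protocol and SAP*

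**What the plan says.** **Entry.** Section 4.1 requires "AST and ALT levels $\leq 2.5 \times$ ULN" and gives no exception for liver metastases. Section 4.2, in the bullet on hepatic impairment during dose escalation, says that "patients with liver metastases with AST/ALT ≤ 5 x ULN can be included in the study". Appendix 6 Table 1 allows AST and ALT up to 5 x "ULN (for subjects with documented metastatic disease to the liver". The bilirubin limit is 1.5 x ULN. Renal entry is an estimated creatinine clearance of at least 30 mL/min "according to the Cockcroft-Gault formula (or local institutional standard method").

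**Hepatic rows of Appendix 6 Table 4.** AST or ALT above 3.0 and up to 5 x ULN is Grade 2. Avelumab is withheld, liver tests are repeated every 3 days, and treatment resumes on return to Grade 1 or below. The follow-up column adds: "If elevations persist $> 5$ to 7 days or worsen: Treat as Grade 3 to 4". The Grade 3 to 4 row begins "Permanently discontinue avelumab therapy" and adds corticosteroids.

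**Renal rows of the same table.** The Grade 2 to 3 band is "Creatinine increased $> 1.5$ and $\leq 6$ x ULN". The action is to withhold avelumab and give corticosteroids, with resumption after return to Grade 1 or below.

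**Baseline elsewhere.** Section 5.6.2.13 states: "The threshold of laboratory abnormalities for a potential DILI case depends on the subject's individual baseline values and underlying conditions". The liver-enzyme exception in the DLT definition (Section 3.3.1) accepts a return to baseline. Sections 5.6.1.1 and 5.6.2.6 tie adverse events to worsening, and the diarrhea rows of Table 4 count stools over baseline. The hepatic and renal rows contain nothing of this kind.

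**The concern.** One part of the protocol admits a patient on a given laboratory value, and another part acts on the same value as an immune-related reaction. For AST/ALT in patients with liver metastases, that action ends in permanent loss of avelumab and a steroid course, although nothing has changed since entry. The hepatic and renal rows do not say that the value must be new or worse than at entry.

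At stake are consistency between sites and the treatment actually delivered. One investigator may follow Table 4 as written and stop avelumab. Another may treat the value as baseline and continue. Section 7 defines patients evaluable for response as those who received at least one cycle. It does not say how to treat a patient who lost one of the three drugs within that cycle, so the response rate attributed to the triplet may include such patients.

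**Working it through.** The plan states no figure on this point, so there is none to reproduce. The check compares the entry ranges with the action bands.

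**Step 1. AST/ALT and bilirubin (multiples of ULN)**

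| Test | Entry range | Withhold band | Overlap |
|---|---|---|---|
| AST/ALT, Section 4.1 | up to 2.5 | above 3.0 to 5 | none |
| AST/ALT with liver metastases, Section 4.2 and Appendix 6 Table 1 | up to 5 | above 3.0 to 5 | above 3.0 to 5, the whole band |
| Bilirubin | up to 1.5 | above 1.5 to 3 | none (limits touch) |

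The liver-metastasis exception adds 5 - 2.5 = 2.5 ULN units. The overlap is 5 - 3.0 = 2.0 units, and 2.0 / 2.5 = 80%. This is a share of the range, not of patients.

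**Step 2. A patient stable at 4 x ULN.** Chemistry is tested weekly in cycle 1 (Sections 3.3.1 and 5.4). Suppose the row is first applied on Day 8. With repeats every 3 days, the same value is seen on Days 11, 14 and 17, which are 3, 6 and 9 days later. The 5-to-7-day persistence window has passed by Day 17, inside the first 28-day cycle. To resume, the patient would have to fall to 3.0 x ULN, which is (4 - 3.0) / 4 = 25% below the entry value. From 5 x ULN the required fall is (5 - 3.0) / 5 = 40%. An unchanged value, or one that rises slightly, cannot satisfy this.

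**Step 3. Creatinine.** Inverting Cockcroft-Gault at the entry limit gives

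creatinine = (140 - age) x weight x (0.85 if female) / (72 x 30).

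The documents give no creatinine ULN. Assumed: 1.2 to 1.3 mg/dL for men and 1.0 to 1.1 mg/dL for women.

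- Man, 65 years, 70 kg: 75 x 70 / 2160 = 2.43 mg/dL, or 1.87 to 2.03 x ULN. In the withhold band.
- Woman, 65 years, 70 kg: 2.43 x 0.85 = 2.07 mg/dL, or 1.88 to 2.07 x ULN. In the withhold band.
- Man, 75 years, 50 kg: 65 x 50 / 2160 = 1.50 mg/dL, or 1.16 to 1.25 x ULN. Grade 1, avelumab continues.

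Over ages 45 to 80 and weights 50 to 90 kg, the range at clearance 30 is 1.07 x ULN (man, 80 years, 50 kg, ULN 1.3) to 3.36 x ULN (woman, 45 years, 90 kg, ULN 1.0).

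The clearance at which creatinine equals 1.5 x ULN is (140 - age) x weight x (0.85 if female) / (72 x 1.5 x ULN). For the 65-year-old man of 70 kg this is 5250 / 129.6 = 40.5 mL/min (ULN 1.2) or 5250 / 140.4 = 37.4 mL/min (ULN 1.3). For the woman it is 4462.5 / 108 = 41.3 (ULN 1.0) or 4462.5 / 118.8 = 37.6 (ULN 1.1). Such patients, if eligible with clearance from 30 to roughly 37 to 41 mL/min, already lie in the withhold band.

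**The case against.** **Table 4 manages reactions, and an unchanged value is not a reaction.** Section 5.6.1.1 requires an untoward occurrence or a worsening. Section 5.6.2.6 reports mandated laboratory results only on deterioration from baseline, and only under further conditions. This is the strongest reply, and it stands for the counting of events. It does not settle treatment: those sections govern reporting, while the hepatic and renal rows give treatment actions and do not refer to them. A trivial rise from 4 x ULN would count as worsening, and the patient still could not reach the resume condition.

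**The main inclusion criterion is 2.5 x ULN.** If it governs, the AST/ALT overlap disappears. That is correct, and it makes the point conditional. But Section 4.2 and Appendix 6 Table 1 admit these patients explicitly, so the conflict over entry has to be settled as well.

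**The rows do contain repeat testing and work-up.** The Grade 2 row repeats tests every 3 days and escalates only on persistence or worsening. The Grade 3 to 4 row lists specialist consultation, imaging and biopsy. This protects against a single stray value. It does not protect a patient with a stable elevation, because persistence is exactly what repeat tests will show.

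**The renal limb rests on an assumed ULN and on body size.** It does, and small or elderly patients at clearance 30 may be in Grade 1. The limb is therefore stated as conditional.

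**Conclusion.** The conflict is in the text for AST/ALT. If the 5 x ULN limit governs, every eligible patient with liver metastases and a stable value above 3 and up to 5 x ULN meets the withhold rule, then the permanent-stop rule, and cannot meet the resume condition. If 2.5 x ULN governs, nobody does so on an unchanged value. For creatinine, the overlap affects many but not all patients near the entry limit, depending on age, weight, sex and local ULN. The documents do not say how many patients will enter in either range, so the effect on the trial as a whole is unknown.

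A reader might infer more than this, in four ways that the documents do not support:

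- *Bilirubin has the same problem.* It does not. The limits touch at 1.5 x ULN, and an unchanged eligible value above ULN is Grade 1, for which avelumab continues.
- *Renal patients lose avelumab permanently.* The Grade 2 to 3 renal row says withhold. Permanent loss would have to come through another row, such as the one on prednisone of 10 mg per day or more for over 12 weeks.
- *Reported toxicity of the triplet is inflated.* This is not shown. Adverse event reporting is tied to worsening, and DLTs need clinical significance, at least possible relation to drug and committee confirmation, with a baseline exception for liver enzymes.
- *A given percentage of patients will cross 5 x ULN by chance.* That would need a baseline distribution and a visit-to-visit variability, and the documents give neither.

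**What to change.** Reconcile three sets of text: the entry limits (Sections 4.1 and 4.2, Appendix 6 Table 1), the hepatic and renal rows of Appendix 6 Table 4, and the baseline-referenced rules in Sections 5.6.1.1 and 5.6.2.6. The aim is that an unchanged, eligible baseline value does not by itself meet an action row. Which limit or rule changes is for the sponsor to decide.

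In the safety report, tabulate patients with abnormal liver or renal values at baseline separately.

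A rule that counts an event or DLT only when the CTCAE grade exceeds the baseline grade is not recommended. The DLT exception and Section 5.6.2.13 refer to baseline values, not grades. Such a rule would also ignore a rise from 3.1 to 4.9 x ULN (4.9 / 3.1 = 1.58, a 58% increase), because both values are Grade 2.

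The cost is a wording amendment and a little extra tabulation. Baseline values are already collected.
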